### *The Positive and Negative Syndrome Scale (PANSS)*

The PANSS is the primary assessment instrument for psychopathology. The PANSS contains 30 items that assess symptoms of psychotic disorders including positive, negative and general psychopathology. The PANSS was chosen because of its widespread use in clinical studies of psychosis, and its demonstrated reliability in assessing psychopathology across diverse patient populations.

### *Diagnostic Interview*

The Structured Clinical Interview for DSM-5 (SCID-5-RV) will be used to confirm the diagnosis of a psychotic disorder and/or rule out other diagnoses. The SCID-5-RV is a semi-structured interview designed to evaluate DSM-5 Axis I diagnoses.

### *Clinical Global Impressions Severity Scale (CGI-S)*

The CGI-S is used for repeated evaluations of global psychopathology. The CGI-S scale is widely used in schizophrenia research and is a single 7-point Likert scale rating severity of psychopathology on a scale of 1 (normal, not ill) to 7 (very severely ill).

### *Clinical Global Impressions Severity Improvement Scale (CGI-I)*

The CGI-I is used to assess the clinical change as compared to symptoms at baseline using a 7-point Likert scale, ranging from very much improved (1) to very much worse (7).

### *Abnormal Involuntary Movement Scale (AIMS)*

The AIMS is a 12-item scale designed to record the occurrence of dyskinetic movements. Items 1 to 10 are rated on a 5-point scale, with 0 being no dyskinetic movements and 4 being severe dyskinetic movements. Items 11 and 12 are yes/no questions regarding the dental condition of a subject.

### *Magnetic Resonance Imaging (MRI) Procedures*

MRI will be performed at the IU Center for Neuroimaging using an integrated 45-minute exam, including structural and fMRI. Scans will be completed on a research-dedicated Siemens MAGNETOM Prisma 3T scanner. First, we will conduct a high-resolution 3D magnetization

prepared rapid gradient echo (MPRAGE) scan for individual anatomical reference, comprised of 160 sagittal slices with 1.0x1.0x1.2 mm voxel dimension. Subjects will practice tasks on a personal computer during Visit 1 and prior to the scan at subsequent visits. An MRI-compatible response box will be utilized for tasks, recording reaction time and accuracy. Functional scans will be acquired using T2\*-weighted gradient spin echo-planar imaging (EPI) sequence with TR/TE 1200/29 ms for 54 axial slices and voxel size of 2.5x2.5x2.5 mm. fMRI will employ scene encoding and recognition EM paradigms, shown by our group and others to demonstrate reliable precuneus activation during cognitive functions of interest. We have successfully implemented all tasks in multiple studies of patients with psychosis. A task-free resting state fMRI scan will also be acquired to measure functional connectivity between precuneus and associated structures and circuits.

#### **Scene Encoding and Recognition Tasks:**

These tasks utilize stimuli and a task design modified from that used by Detre et al. in EM studies in temporal lobe epilepsy. We will be using methods identical those in our previous work. During encoding task, subjects view complex scenes one at a time and are instructed to remember each for later recognition testing (Fig. 3). Images are shown in a block design with interleaved 36-s image and control blocks. Image blocks consist of nine consecutive images, each displayed for 3.5 s, with an inter-stimulus interval (ISI) of 500 ms. A total of 36 scene images are shown. Control blocks consist of a retiled image, repeatedly displayed at the same rate. Subjects do not press buttons during the encoding phase. The recognition task is a separate event-related fMRI paradigm administered immediately after the encoding phase. During the recognition task, subjects are shown the 36 scenes from the encoding phase intermixed with 36 new scenes. These images will be displayed consecutively in a pseudorandomized manner, each for 3.5 s with an ISI of 500 ms. Subjects are instructed to indicate, via button press, whether each displayed image was previously seen (target) or new (foil). Button-press responses are recorded to assess reaction time and accuracy. Task length for each trial is 5:15. Different versions of the scene encoding and recognition EM tasks will be utilized, with order of administration randomized, to mitigate the potential impact of learning effects.

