**Fig 1. Study Outline**

#### *rTMS Set up and Administration*

rTMS will be delivered using the Magventure MagPro X100 Magnetic Stimulator (Magventure Inc., Alpharetta, Georgia). Motor threshold (MT) will be determined using single pulse stimulation over the left primary motor cortex, assessed as the lowest intensity producing five visible movements of the right abductor pollicis brevis out of ten stimulations. The Magventure MagPro X100 is equipped with a research-dedicated coil with combined active and sham stimulation capabilities. The active and sham functions share the same acoustic properties and sham mimics cutaneous stimulation, facilitating double-blinding. Study conditions (20 Hz, 1 Hz, sham) will be assigned a label, such as A, B, or C, by a non-blinded staff member who is not directly involved with the research team. Subjects will be assigned a sequence of blinded study conditions in randomized and counterbalanced fashion.

**High Frequency rTMS:** High frequency rTMS, or rTMS greater than 5 Hz, leads to facilitatory effects on brain excitability. Previous studies have demonstrated that administration of as little as a single train or a small number of trains are able to produce an immediate increase in cortical excitability. Additionally, earlier investigations have utilized high frequency rTMS in schizophrenia populations, demonstrating that the treatment is safe, well-tolerated and capable of altering cognitive performance. Our group has employed 20 Hz rTMS at 110% of motor threshold in a stimulation protocol in-line with the current proposal to improve cognitive function in an EPP cohort. **High Frequency rTMS Protocol:** Subjects will receive one session of high frequency rTMS within the following stimulation parameters: 20 Hz, at 120% of MT, 60 trains (1.0 second per train), 20 pulses per train, inter-train interval of 15 seconds, for a total of 1200 pulses over 16 minutes.

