## **13.0 Statistical Considerations**

### **Analyses**

#### *Power Analyses*

In terms of the power to detect a significant effect of precuneus directed rTMS on EM performance or neurocircuitry, there are no known calculations with EPP patients. We plan to enroll 30 subjects and anticipate a 20% drop out rate, thus yielding 24 completers. This is consistent with our previous clinical trial efforts in early phase psychosis populations, including a study of adjunct rTMS for cognitive impairment and negative symptoms. For all planned analyses, a total of 24 subjects in a cross-over design will result in 0.8 power to detect an assumed treatment difference at medium effect size 0.6; using an alpha level of 0.05 and conservatively assumed a within-subject correlation of 0.5. As no previous precuneus rTMS pilot study was available, this standardized effect size of 0.6 is considered to a conservative estimate to detect the significant results.

[figure not shown]

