#### *Statistical Analyses*

[figure not shown]
Intent-to-treat (ITT) analysis will be conducted, and thus all randomized subjects will be included. ITT is the most conservative approach for detecting a treatment effect, because the inclusion of subjects who do not complete the intervention will serve to underestimate rather than overestimate any treatment effect. Sensitivity analyses including a subset analysis using a “completers only” analysis will be performed to test the robustness of the findings. Statistical tests will be performed based on two-sided test at the 5% level of significance.

Descriptive characteristics at baseline will be summarized for the whole sample. For continuous variables, the mean and standard deviation will be presented. For categorical variables, the number and percent will be reported.

Primary analyses: For each subject, change scores in activation of the precuneus (aim 1), functional connectivity (aim 2), and EM performance (aim 3) will be calculated at each treatment by using (post - baseline). We will employ a mixed model for repeated measures ANCOVA, of the general form for each measure:  $change_{ijk} = \mu + \alpha_i + b_{ij} + \gamma_k + \beta X_{ijk} + \tau_d(i, k) + e_{ijk}$ , where  $\mu$  is overall mean;  $\alpha_i$  is the effect of the  $i$ th treatment sequence ( $i = 1, 2, \dots, 6$ );  $b_{ij}$  is the random effect with variance  $\sigma_b^2$  for the  $j$ th subject ( $j = 1, 2, \dots, 24$ ) of the  $i$ th treatment sequence;  $\gamma_k$  is the period effect ( $k = 1, 2, 3$ );  $\beta X$  is the baseline value;  $\tau_d(i, k)$  is the direct effect of the treatment administered in period  $k$  of sequence group  $i$ ; and  $e_{ijk}$  is the random error with variance  $\sigma^2$  for the subject in period  $k$ . Based on this model, we will compare the treatment difference in change score between 1 Hz and Sham as well as 20 Hz and Sham. Under the assumption of missing at random, this mixed effect model will provide the unbiased estimates.

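### EM task version is neither stated to be balanced against stimulation condition nor included in the model; balancing it and adding a version term is a cheap gain in precision (low severity)

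*Combined protocol and SAP*

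**What the plan says.** Section 6.0, Scene Encoding and Recognition Tasks, says of the EM task: "Different versions of the scene encoding and recognition EM tasks will be utilized, with order of administration randomized". The stated purpose is to limit learning effects. The section gives no number of versions, no evidence that they are equally difficult, and no link between version order and stimulation order.

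Counterbalancing is promised only for stimulation, in Section 3.0, rTMS Set up and Administration: "Subjects will be assigned a sequence of blinded study conditions in randomized and counterbalanced fashion".

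Section 13.0, Statistical Analyses, sets the model: "We will employ a mixed model for repeated measures ANCOVA, of the general form for each measure". Its terms are treatment sequence, random subject, period, baseline value, treatment and error. The mediation models and the imaging analyses add no term for task version. On the comparisons: "we will compare the treatment difference in change score between 1 Hz and Sham as well as 20 Hz and Sham".

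Attachment 1 schedules the EM task four times, once at Visit 1 and once after stimulation at each of Visits 2 to 4.

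**The concern.** In this cross-over the treatment comparison is made within subjects. A subject's 1 Hz score and sham score come from two different scene sets. If one set is harder, that difference enters the 1 Hz minus sham difference directly. Randomising version order stops this from becoming a systematic error, but it does not remove the noise.

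The precision of the two treatment contrasts is at stake, most clearly for EM performance. Task activation may be affected too, because it is estimated from correct trials in the same scene sets. Functional connectivity is not, because Section 6.0 takes it from a task-free scan. The planned power is 0.80 with no margin, and Section 13.0 says that no earlier precuneus study was available to support the effect size.

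**Working it through.** **Inputs from the documents.** Section 13.0, Power Analyses: "a total of 24 subjects in a cross-over design will result in 0.8 power"; "assumed treatment difference at medium effect size 0.6"; "using an alpha level of 0.05 and conservatively assumed a within-subject correlation of 0.5". Statistical Analyses: "Statistical tests will be performed based on two-sided test at the 5% level of significance".

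**Reproducing the stated power.** With outcome SD 1 and correlation 0.5, the SD of a within-subject difference is √(2 × (1 − 0.5)) = 1. The noncentrality is 0.6 × √24 = 2.94. A two-sided paired t-test on 23 df gives power 0.804, so the stated 0.80 is reproduced.

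**The planned cross-over model.** The 24 subjects give 72 scores. Subjects (24), periods (2) and treatments (2) use 28 parameters, leaving 44 residual df. Within-subject error variance is 1 − 0.5 = 0.5, so the contrast SE is √(2 × 0.5/24) = 0.204 and power is 0.820.

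**Adding version noise (assumption).** Let S be the between-version SD in outcome-SD units. The documents give no value. If version noise comes on top of the planned error and is not modelled, SE = √(2 × (0.5 + S²)/24), still on 44 df:

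| S | Error variance | Increase | Power, version ignored | Power, version balanced and in the model |
|---|---|---|---|---|
| 0 | 0.50 | 0% | 0.820 | 0.819 |
| 0.1 | 0.51 | 2% | 0.812 | 0.819 |
| 0.2 | 0.54 | 8% | 0.790 | 0.819 |
| 0.3 | 0.59 | 18% | 0.754 | 0.819 |

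Simulations of the unadjusted analysis (3,000 or 4,000 trials per setting) gave 0.78 to 0.80 at S = 0.2 and 0.75 to 0.76 at S = 0.3.

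**The other reading.** If the planned 0.5 already contains version noise, removing it leaves an error variance of 0.5 − S². Balanced adjustment then raises power from 0.820 to 0.849 at S = 0.2 and to 0.887 at S = 0.3.

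**Validity as planned.** With random, unadjusted versions, simulated type I error was 0.048 to 0.051, and the mean estimate for a true effect of 0.6 was 0.594 to 0.601. The test and the estimate are sound.

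**Version term without balance.** With four versions in random order for each subject, adjusting inflates the contrast variance by 1.08 on average (5th to 95th percentile 1.01 to 1.21). Power is then about 0.79 whatever S is. This cost comes from uneven assignment, not from the version term itself.

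**Balance without the version term.** The contrast is then free of version noise, but the residual variance still contains it, so the test is conservative. Simulated type I error was 0.031 at S = 0.3.

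**Balance with the version term.** Label the conditions A, B, C and the post-stimulation versions 1, 2, 3. One layout over the six sequences is A1 B2 C3; B3 C1 A2; C2 A3 B1; A1 C2 B3; C3 B1 A2; B2 A3 C1. Each condition meets each version twice in six subjects, so 2 × 4 = 8 times in 24. Each version also falls 8 times in each period. The contrast variance is not inflated (factor 1.00). Residual df go from 44 to 42, and power at S = 0 from 0.820 to 0.819.

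**The case against.** Five points can be made for the plan as written.

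- **Allocation.** A reader might infer that versions are randomised independently of stimulation. The documents do not say so; they say only that version order is randomised. An unpublished list could already cross the two. This stands: the supportable statement is that balance is not specified. The missing model term remains in either case.
- **Size.** A reader might infer that the trial falls short of its planned power. That requires version noise to lie outside the planned error, and the planned correlation of 0.5 may already describe observed scores. It also requires a sizeable version SD. Each recognition score rests on 72 scenes (36 old, 36 new), so scene-level differences should partly average out. Nothing in the documents supports a value as large as 0.5. This stands, so both readings of the error are shown and the range stops at 0.3.
- **Validity.** A reader might infer bias or a misleading test. The simulations show neither. Chance imbalance of versions between conditions is also not a second harm: it is the same noise, seen in a single trial.
- **Activation.** The activation contrast compares correct targets with correct foils within the same scan, which may remove some of a version's difficulty. This stands: the effect on activation is less certain than on EM performance.
- **Purpose.** This is a pilot with an unbiased design, so the point should not be ranked high. That is accepted and sets the severity. It does not remove the case for a change that costs almost nothing.

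**Conclusion.** The point holds as a cheap improvement of low severity. The plan does not state that task version is balanced against stimulation condition, and its model has no version term, so any version differences stay in the within-subject error for EM performance and possibly for task activation.

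The plausible loss is about 0 to 3 points of power for version SDs up to 0.2, and about 7 points at 0.3. These figures are for one contrast at effect size 0.6 with 24 completers, and they assume that version noise adds to an error variance of 0.5. If the planned error already includes it, planned power is unaffected and the change is a gain. If the versions are equally difficult, nothing is lost. The documents do not show which case applies, and they do not support a claim of bias, of an invalid test or of an underpowered trial.

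**What to change.** 1. **Allocation.** State how many versions exist and how they are assigned. Assign the three post-stimulation versions so that each appears equally often with each condition and in each period across the six sequences, for example by the layout shown in the working.
2. **Model.** Add version as a fixed effect in the mixed model for EM performance and task activation. Leave the connectivity model unchanged.

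Do both, because balance alone makes the test conservative. If versions are already crossed with condition, say so; only the second step is then needed.

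A common baseline version is optional. The baseline version is shared by all three of a subject's change scores and cancels from the treatment contrasts. Using one version for everyone would tie the raw change within each condition to a fixed version difference, which matters for descriptive summaries. If four versions rotate through all four scans instead, crossing four Latin-square version orders with the six sequences (24 subjects) gives the same balance, with 41 residual df and power 0.819.

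**Cost.** One column in the randomisation list and one model term. With three post-stimulation versions, residual df fall from 44 to 42, and power from 0.820 to 0.819 if versions are equal. Dropout from 30 to 24 will leave slight imbalance; even fully random order with the term costs only about 3 points.

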#### *Positioning and motion*

Subjects are instructed to remain still during scanning and deformable foam cushioning is used to stabilize the head. Real time image reconstruction and processing are used for quality assurance at the time of scanning. For fMRI, minor subvoxel-level translation or rotation is adjusted during post-processing. Noise: Noise-attenuating headphones and ear stopples provide excellent noise reduction and permit adequate auditory perception.

#### *Functional Imaging Stimulation and Physiological Monitoring Procedures*

A comprehensive physiological monitoring system will be used with synchronized digital recording including pulse oximeter, respiratory belt, HR and BP measures, which will be available for analysis in relation to BOLD fMRI time series.

**Figure 3. Scene Encoding and Recognition EM Task**

## **7.0 Safety Assessments**

### *Vital Signs*

A seated blood pressure and pulse will be assessed at study visits per Study Procedures Table (Attachment 1).

### *Medical History*

The subject's lifetime medical history will be taken during the screening period. Medical history includes previous and current diseases.

### *Physical Examination*

A physical examination including a neurological examination will be conducted as outlined in the Study Procedures Table.

## **8.0 Laboratory Assessments**

A urine pregnancy test will be conducted in all female subjects, and a urine drug screen will be conducted in all subjects, as outlined in the Study Procedures Table.

## **9.0 Concomitant Medication**

See Attachment 2.

## **10.0 Adverse Events**

Adverse events (AEs), especially those for which the relationship to study treatment is not "unrelated," will be followed up until they have returned to baseline status or stabilized at the discretion of the PI. If after the follow-up period, return to baseline or stabilization cannot be established an explanation will be recorded in the source documentation.

## **11.0 Criteria for Repeat Assessments, Rescreening, and Discontinuation**

### *Repeat Assessments*

Screening assessments can be repeated within the screening window under the same screening number with the exception of eligibility criteria related rating scales/questionnaires. Subject diagnosis confirmation will not be repeated.

### *Rescreening*

Subjects who screen fail may be rescreened one time, under the same screening number. If a subject is rescreened, all screening assessments (with the exception of the diagnosis confirmation) must be repeated and the stability criteria timelines must be met.

### *Discontinuation*

Subjects will be discontinued under the following circumstances:

1. During the course of the study, subjects with an interruption of stimulation administration
2. Subjects unwilling or unable to complete study assessments or procedures
3. Subjects who experience seizure occurrence at any point during study participation
4. Subjects who require a change in dose of antipsychotic medication or the addition of a new antipsychotic medication

5. Subjects experiencing an exacerbation of illness requiring an increased level of care or one judged to be clinically significant by the PI.

If subjects discontinue from the study, completion of discontinuation assessments will be at the discretion of the PI. A subject may withdrawn from the study at any time at his/her own request, or may be withdrawn at any time at the discretion of the PI for safety, behavioral, or administrative reasons.

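### Outcomes need not be collected for interrupted and later sessions, so including non-completers does not make the ITT estimate conservative

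*Combined protocol and SAP*

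**What the plan says.** Section 11.0 (Discontinuation) names five circumstances in which a subject is discontinued. The first is "During the course of the study, subjects with an interruption of stimulation administration". On data collection afterwards it says only: "If subjects discontinue from the study, completion of discontinuation assessments will be at the discretion of the PI".

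Attachment 1 places the post-stimulation MRI and EM task at Visits 2, 3 and 4, the same visits as stimulation. It has no early-termination column. Visit 5 covers adverse events and concomitant medication only. Section 3.0 has the scan follow directly after each session and does not say what happens when a session is cut short.

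Section 13.0 (Statistical Analyses) defines the analysis set: "Intent-to-treat (ITT) analysis will be conducted, and thus all randomized subjects will be included". It calls this conservative because "the inclusion of subjects who do not complete the intervention will serve to underestimate rather than overestimate any treatment effect". The model is a mixed model for change scores with sequence, period, treatment, baseline and a random subject effect. The plan gives no imputation rule, and says of the model: "Under the assumption of missing at random, this mixed effect model will provide the unbiased estimates". The only sensitivity analysis it names is completers-only.

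**The concern.** ITT dilutes an effect when people who received incomplete treatment are still measured and are analysed under the assigned condition, or when their missing values are imputed conservatively. This plan requires neither. A subject can be counted in the ITT set while the sessions that would do the diluting have no outcome.

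Each condition is given once, so a lost session is that subject's only observation on that condition. The three conditions differ physically (20 Hz trains, a continuous 1 Hz train, sham), so equal interruption rates cannot be presumed. If interruption is related to how the subject would have responded, the active-versus-sham contrast can shift in either direction. A reader relying on the stated property would take a positive result as a lower bound when it is not one.

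**Working it through.** **Inputs from the documents.** 30 enrolled, 20% dropout from all causes, 24 completers, effect 0.6, within-subject correlation 0.5, two-sided 5% test (Sample Size in section 3.0; section 13.0). One session and one post-session scan per condition (section 3.0; Attachment 1). The documents give no interruption rate and no information on why sessions would be interrupted, so everything on those two points below is assumed.

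**Step 1: the plan's own figure.** 30 × (1 − 0.20) = 24. The SD of a paired difference is √(2(1 − 0.5)) = 1, the noncentrality is 0.6 × √24 = 2.94, and with 23 df the power is 0.804, against the stated 0.8. It reproduces and is not in dispute.

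**Step 2: what is left after an interruption**, if neither that session nor later ones are scanned.

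| Interrupted in | Change scores kept | Contribution |
|---|---|---|
| Session 1 | 0 | None |
| Session 2 | 1 | Enters the model; no within-subject contrast |
| Session 3 | 2 | One within-subject contrast; active versus sham unless sham was the third session |

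Illustration: if the 6 expected dropouts were spread evenly, two per session, they would keep 2×0 + 2×1 + 2×2 = 6 of 18 planned scores, and 4 of the 6 subjects would still contribute.

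**Step 3: direction of bias.** The section 13.0 model was used in simplified form: sequence, period, treatment and a random subject intercept, with no baseline covariate. Total variance is 1 and correlation 0.5, so the residual variance is 0.5 (SD 0.707). The interrupted session and all later ones are missing. The true 20 Hz minus sham effect is 0.6.

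Suppose the fraction p of 20 Hz sessions with the poorest session-specific response is lost. The mean residual of the retained 20 Hz sessions is then 0.707 × φ(z)/(1 − p), where φ(z) is the standard normal density at the p-quantile. That shift passes directly into the treatment estimate.

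- p = 0.20: 0.707 × 0.280/0.80 = 0.247, giving 0.6 + 0.247 = 0.847.
- p = 0.10: 0.707 × 0.1755/0.90 = 0.138, giving 0.6 + 0.138 = 0.738.
- If the best responders are lost instead, the sign reverses: 0.353 and 0.462.

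A simulation of the same model with 400,000 subjects per scenario agrees:

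| Assumed mechanism | True 0.6 | True 0 |
|---|---|---|
| About 20% dropout unrelated to outcome | 0.60 | 0.00 |
| Poorest 10% of 20 Hz sessions interrupted | 0.74 | +0.14 |
| Poorest 20% interrupted | 0.85 | +0.24 |
| Best 10% interrupted | 0.46 | −0.14 |
| Best 20% interrupted | 0.35 | −0.25 |

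Under dropout unrelated to outcome there is no underestimation. Under response-related interruption the error takes either sign.

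**Step 4: completers-only.** In these scenarios every completer has a 20 Hz session drawn from the same truncated distribution, so the shift of 0.247 at p = 0.20 carries over unchanged. Agreement between the two analyses would not reveal the problem.

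**The case against.** The strongest reply is that the plan loses less than it may seem to. A reader might infer that interrupted subjects have no outcome at all in the ITT set. The documents do not support that. Scores are taken after each of three sessions, the mixed model uses every observed score, and only an interruption in session 1 can leave none. Discontinuation assessments are optional, not excluded, and section 11.0 does not cancel the scan that section 3.0 places directly after the session. Some outcomes may therefore exist, though collected selectively.

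A reader might also infer that the ITT and completers-only results must agree by construction. They need not: the mixed model keeps partial data that completers-only discards, and subjects leave for other reasons after valid sessions. The narrower statement stands: both lack the interrupted sessions.

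The term *interruption* is undefined. It could mean a session stopped part-way or a break in the weekly series, and in the second case a same-visit scan would recover nothing.

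Finally, section 13.0 already states missing at random, and in a mechanistic pilot the effect of full stimulation is a defensible target. Both points are fair. Neither rescues the conservativeness sentence. A claim of underestimation and a claim of unbiasedness can be reconciled only if outcomes after incomplete stimulation are in the data, and the plan does not require them.

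**Conclusion.** The point holds in limited form and should be corrected. Outcomes for interrupted and later sessions need not be collected, so the claim that including non-completers underestimates the effect does not hold. The estimate's unbiasedness rests on missing at random. If interruption is related to response, it can be wrong either way: illustratively 0.35 to 0.85 around a true 0.6 with 20% interrupted, and 0.46 to 0.74 with 10%. These ranges depend on assumed mechanisms, the omitted baseline covariate and assumed rates. The real effect could be negligible.

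A reader might infer that the plan overstates the effect by a known amount. For example, if k of 30 interrupted active sessions had zero effect, the as-randomised effect would be 0.6(30 − k)/30. The ratio 30/(30 − k) − 1 is then 3% for k = 1 and 25% for k = 6. The documents do not support that. They give no interruption rate, and the 20% dropout covers all causes. Section 3.0 itself says that one or a few high-frequency trains can raise excitability, which conflicts with assuming no effect of partial 20 Hz stimulation. The figure also compares two different target effects. Overestimation is possible, not shown.

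**What to change.** In section 13.0 (Statistical Analyses):

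- Delete the sentence on underestimation. State that sessions without a scan contribute nothing and that the estimates rest on missing at random.
- Report how many randomized subjects contribute to each contrast (1 Hz versus sham, 20 Hz versus sham).
- Add a delta-adjusted sensitivity analysis that allows missing not at random. Completers-only can stay, but not as the test of this assumption.

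Across sections 3.0, 11.0, 13.0 and Attachment 1, reconcile what *interruption* means and whether *discontinued* applies to stimulation only or to all remaining scans. This is a request for consistency, not for a particular clinical rule.

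Leaving the stopping rule and the investigator's safety judgement unchanged, state that the post-stimulation scan already scheduled for that visit is sought for outcome purposes where feasible. Record the pulses delivered, and analyse any such scan under the assigned condition in the ITT analysis.

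The cost is wording in two sections, a footnote to Attachment 1 and one further analysis. The scan is already scheduled for the visit. The drawback is that a few partially stimulated scans may slightly dilute the estimate.
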